5.3 Tolerability and safety objectives

The study product safety and tolerability will be evaluated.

6. Design of the clinical investigation

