7.3 Statistical Analysis

Descriptive statistics of all relevant variables will be performed. Continuous variables will be summarized by the number of patients (N), mean, standard deviation, median, minimum, maximum. Where appropriate, 95% confidence intervals for the target variables will be estimated. Categorical variables will be summarized by the number (N) and the proportion of patients (%).

The significance level of statistical tests will be set at 0.05. Details of statistical analysis are provided in the following paragraphs.

The statistical analysis will be performed using SAS 9.4 for Windows (SAS Institute Inc., Cary, NC, USA).

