## 7. SAMPLE SIZE AND STATISTICAL POWER CONSIDERATION

In a previous observational study, 38.2% of the patients treated with SOC preemptive treatment according to MASCC guidelines did not reach G2 radiation dermatitis at week 5. In a pilot study using Xonrid®, the proportion of patients treated with Xonrid® and SOC preemptive treatment according to MASCC guidelines that did not reach G2 radiation dermatitis at week 5 was 82.9%.

According to these previous results, a two group chi-square test with a 0.05 two-sided significance level would have had 80% power to detect the difference between a proportion of patients that do not reach G2 of 38.2% in the Group B (standard of care (SOC) preemptive treatment according to MASCC guidelines) and a proportion of 82.9% in the Group A (Xonrid® and SOC preemptive treatment according to MASCC guidelines) when the sample size in each group is 18. To take into account a possible 10% dropout rate, 20 patients in each treatment group have been enrolled. As two cancer sites have been investigated, to assess the treatment effect within each site, 80 patients have been enrolled: 40 patients with breast cancer and 40 patients with head and neck cancer.

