## 9. GENERAL ISSUES FOR STATISTICAL ANALYSIS

### 9.1 Definitions, Derived Variables and Datasets

Analyses will be performed and report separately for each cancer site (i.e., breast cancer and head and neck cancer).

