## 12. SAFETY EVALUATION

### 12.1 Extent of Exposure

### 12.2 Adverse Events

Adverse events will be coded according to MedDRA, version 21.1. AEs will be summarized by treatment arm in terms of the number of patients who experienced at least one AE, study product-related AE, serious AE, severe AE and the number of patients withdrawn due to AE will be summarized. The comparisons will be analyzed using chi-square test. For each SOC and preferred term, summaries will be made with respect to the proportion of patients having at least one occurrence of that event during the trial and the total number of events.

```
proc freq;
table treatment * cat_variable / CHISQ;
run;
```

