### 12.3 Other safety endpoints

Tolerability assessment will be based on the evaluation of site administration adverse events.

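### Adverse events are compared between arms only by a chi-square p-value at about 20 patients per arm, with no estimate or interval showing how much harm remains possible

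*SAP*

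**What the plan says.** Safety is a stated objective without a hypothesis, margin or acceptance criterion: "The study product safety and tolerability will be evaluated" (protocol 5.3).

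SAP 12.2 summarises AEs by arm "in terms of the number of patients who experienced at least one AE, study product-related AE, serious AE, severe AE", plus withdrawals due to AEs, and then says "The comparisons will be analyzed using chi-square test". The accompanying code is PROC FREQ with the CHISQ option only. Protocol 7.3.6 and SAP 5.3 and 11.5 name the same test.

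On tolerability, SAP 12.3 adds "Tolerability assessment will be based on the evaluation of site administration adverse events", with no summary measure.

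SAP 9.1 sets the level of analysis: "Analyses will be performed and report separately for each cancer site". The safety tables listed in SAP 14.3 follow that split.

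Protocol 7.3 fixes alpha ("The significance level of statistical tests will be set at 0.05") and offers 95% confidence intervals only at discretion. The SAP safety text, its code and the sample table for discrete variables (SAP 14.4.3) do not carry intervals through to AEs. That table has counts, percentages and a p-value. By contrast, the primary endpoint gets an odds ratio with a 95% interval (SAP 11.4.1), and the sample table for continuous variables (SAP 14.4.2) has rows for the treatment difference and its interval.

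**The concern.** The trial was sized for a large efficacy difference. The same group sizes are then used to compare AE frequencies, and the only comparative output specified is a p-value. With about 20 patients per arm, a moderate true excess of AEs on the gel would often give p>0.05. The table would show that p-value beside two percentages, with nothing to tell the reader whether the data rule out an important excess or say little about it. For a preventive gel applied to irradiated skin, local reactions are the harm of most interest. Protocol section 4 already describes earlier experience with the gel favourably on safety, so a sparse table of non-significant p-values could easily be taken as confirmation.

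**Working it through.** **1. The plan's own figure.** SAP 7 states that "a two group chi-square test with a 0.05 two-sided significance level would have had 80% power to detect the difference", with "a proportion of patients that do not reach G2 of 38.2% in the Group B" against 82.9% in Group A, at 18 per group. With the pooled-variance formula and mean proportion (0.382+0.829)/2 = 0.6055:

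n = [1.960·√(2·0.6055·0.3945) + 0.842·√(0.382·0.618 + 0.829·0.171)]² / 0.447² = 17.5, rounded up to 18.

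Drop-out: 18/(1-0.10) = 20. The stated figure reproduces. It targets a 44.7-point efficacy difference; neither document gives a corresponding calculation for safety.

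**2. Group size for safety.** There are 40 patients per site, randomised 1:1 (protocol 6.4.1), and analyses are by site. That gives about 20 per arm.

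**3. Chance of missing an excess.** With a events among 20 gel users and b among 20 controls, the uncorrected Pearson statistic reduces to

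X² = 40(a-b)² / [(a+b)(40-a-b)], significant if X² > 3.841.

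Exact power is the sum of Bin(a; 20, p_gel)·Bin(b; 20, p_control) over all significant tables with a > b. When the control rate is zero, 3 v 0 gives 360/111 = 3.24 (not significant) and 4 v 0 gives 640/144 = 4.44 (significant). Power is then P(a ≥ 4), which is 0.133 at a true rate of 10% and 0.589 at 20%.

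All AE rates below are assumptions.

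| Gel v control | Excess (points) | Missed at 20 per arm |
|---|---|---|
| 10% v 0% | 10 | 87% |
| 15% v 5% | 10 | 85% |
| 20% v 10% | 10 | 86% |
| 30% v 20% | 10 | 89% |
| 15% v 0% | 15 | 65% |
| 20% v 0% | 20 | 41% |
| 25% v 5% | 20 | 56% |
| 30% v 10% | 20 | 64% |
| 40% v 20% | 20 | 71% |

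For 80% power by the formula in step 1, 20% v 10% would need 199 per arm, 15% v 5% would need 141 and 30% v 10% would need 62.

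**4. What an interval would show (illustrative counts).**

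- 3/20 v 0/20: X² = 3.24, p=0.072, not flagged. The Wilson limits are 5.2% to 36.0% for 3/20 and 0% to 16.1% for 0/20. The Newcombe 95% interval for the 15-point difference runs from 0.15 - √[(0.15-0.052)² + 0.161²] to 0.15 + (0.360-0.15), that is -3.8 to +36.0 points.
- 6/20 v 2/20: X² = 40·16/(8·32) = 2.5, p=0.11, not flagged. The Newcombe interval for the 20-point difference is -5.4 to +43.1 points.
- 0/20 in gel users: the exact two-sided 95% upper limit is 1 - 0.025^(1/20) = 16.8%.

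**The case against.** The strongest reply is that the plan contains no faulty decision rule. A reader might infer that p>0.05 is to be taken as showing the gel is safe. The documents do not say so: the objective is only to evaluate safety, and secondary endpoints, among which safety is listed, are called exploratory (SAP 9.3). That stands, and the point is limited to what the output can show.

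The p-value is also not the only safety information. The plan includes per-arm counts and percentages, grouping by severity and relationship, investigator causality grades and AE listings. A reader could derive a risk difference from the counts. That stands too, but the plan should not leave the calculation to the reader.

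The miss rates depend on assumed AE rates. Application-site reactions may be close to zero in an arm that applies no gel, and there 20% v 0% is missed only 41% of the time. This is why the table shows a spread. Pooling both sites to 40 per arm would lower the miss rates (30% v 10%: 37%; 20% v 0%: 3%), but SAP 9.1 plans no pooled analysis, so those figures do not describe this plan.

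A reader might also infer that chi-square is invalid here and should give way to Fisher's exact test. The figures do not support that. At 20 per arm, each arm's expected event and non-event counts sum to 20, so at most two of the four cells can fall below 5. The test's actual size is about 0.003 to 0.053. Fisher's test would miss more: power for 30% v 10% falls from 36% to 24%, and 4/20 v 0/20 changes from p=0.035 to p=0.106.

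Finally, low power for AEs is inherent in an 80-patient study, and intervals will not detect more harms. That is correct. They only show how much uncertainty remains.

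**Conclusion.** The point holds as a gap in reporting. Chi-square is the only between-arm method named in the safety sections, it is applied by site with about 20 patients per arm, and no AE effect estimate or interval is specified beyond the discretionary sentence in protocol 7.3. Across the assumed rates in the table (control 0 to 20%, excess 10 to 20 points), the test misses the excess 41% to 89% of the time, and more than half the time in every row except 20% v 0%. These figures rest on assumed AE rates, 20 patients per arm and an uncorrected two-sided test at 0.05. Which excess would matter clinically is also an assumption, because the documents set no threshold. A non-significant AE comparison is therefore weak evidence on safety. Severity is minor.

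**What to change.** In SAP 12.2 and protocol 7.3.6, and in the AE tables built on the discrete-variable layout of SAP 14.4.3:

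- For each AE summary category that is meaningful in both arms, report the risk difference (Xonrid plus standard of care minus standard of care) with a 95% Newcombe or exact interval, by cancer site.
- Report the rate of application-site AEs and of product-related AEs in gel users with an exact 95% interval. A between-arm difference means little for product-related events when one arm receives no product.
- State that p>0.05 will not be read as absence of harm. Any chi-square p-values that are kept should be labelled descriptive.

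The cost is a few sentences, extra table rows and the risk-difference and exact-interval options in the PROC FREQ step already planned. No new data or patients are needed. The downside is presentational: wide intervals will make the safety statement look less favourable. This is a cheap improvement.

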In a recent pilot study using Xonrid® (*Iacobelli et al. 2016, accepted for publication on "Supportive care Cancer", 02 jan-2016*), the proportion of patients treated with Xonrid® and SOC preemptive treatment that not reached G2 radiation dermatitis at week 5 was 82.9%. Xonrid® use resulted associated with a decrease in the incidence of G3 toxicity and a delay in the development of G2 toxicity when compared to the data from a previous study (historical cohort)¹¹. At week 5, patients with G2 and G3 dermatitis were about 52% and 10% in the historical cohort and 15% and 2% in the pilot study, respectively.

The aim of this clinical investigation is to evaluate if the use of Xonrid® in the prevention and treatment of G2 radiation dermatitis in breast and head & neck cancer patients can be a valid support, when compared to the Standard of Care as defined by MASCC (Multinational Association for Supportive Care in Cancer) guidelines.

Forty women affected by breast cancer and forty men and/or women affected by head & neck cancer, planned to undergo postoperative or curative radiation treatment will be enrolled in this clinical investigation.

4. Risk and benefits of the investigational device and clinical investigation

To date a large variety of products and methods for the prevention of acute radiation-induced skin reactions have been tested but there is not yet a gold-standard approach in the prevention and management of radiation dermatitis.

Xonrid® is an EC-marked medical device that prevents and treats skin symptoms such as erythema, itching, burning sensation and pruritus, induced by radiotherapy or other causes, by restoring the physiological hydration levels of the affected skin areas.

A previous experience on head & neck cancer patients has shown that Xonrid® is safe and well tolerated and is effective in reducing and delaying high-grade radiation dermatitis.

In this study subjects will be randomly allocated to Xonrid® + Standard of Care or Standard of Care alone. The Standard of Care that subjects will be requested to follow is according to MASCC guidelines, that means evidence-based clinical practice guidelines known and recognized worldwide.

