Subjects will receive their planned radiotherapy treatment and will be constantly followed by clinicians. The study visits will be done every week. Participants will undergo a careful, frequent and accurate evaluation of their irradiated area equal if not better than what is the normal practice for subjects undergoing radiotherapy.

In the case a subject allocated to the group “SOC alone” develops a G2 skin toxicity, an additional treatment will be introduced, according to the Investigator’s opinion.

Should a G3 skin toxicity develops the subject will immediately interrupt the study treatment and the study participation. The Investigators will thereafter choose the best treatment for that subject.

In the light of the above, no additional risk arising from the participation to this clinical investigation can be envisioned.

5. Objectives and hypotheses of the clinical investigation

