7.1 Sample Size Determination

In a previous observational study¹¹, 38.2% of the patients treated with SOC preemptive treatment according to MASCC guidelines did not reach G2 radiation dermatitis at week 5. In a pilot study using Xonrid® (*Iacovelli et al. 2016, submitted*), the proportion of patients treated with Xonrid® and SOC

preemptive treatment according to MASCC guidelines that did not reach G2 radiation dermatitis at week 5 was 82.9%.

According to these previous results, a two group chi-square test with a 0.05 two-sided significance level will have 80% power to detect the difference between a proportion of patients that do not reach G2 of 38.2% in the Group B (standard of care (SOC) preemptive treatment according to MASCC guidelines) and a proportion of 82.9% in the Group A (Xonrid® and SOC preemptive treatment according to MASCC guidelines) when the sample size in each group is 18. To take into account a possible 10% dropout rate, 20 patients will be enrolled in each treatment group.

As two cancer sites will be investigated, to assess the treatment effect within each site, 80 patients will be enrolled: 40 patients with breast cancer and 40 patients with head and neck cancer.

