14.3 Adverse Event, Device Deficiency, Adverse Device Effect reporting

The investigator will report to the Sponsor any AEs, Device Deficiencies and ADEs concerning the medical device occurring during the study. He/She will also co-operate with the Sponsor in connection with the reporting of any SADE to the Competent Authority and to the Independent EC, if applicable.

All AEs regardless of severity occurring between recruitment and completion of the study by a subject must be recorded on the AE form provided with the CRF.

If there is a significant worsening of a medical condition that was present before starting the study, this should be considered as a new AE and a complete evaluation recorded.

Signs and symptoms considered as lack of efficacy and occurring during the study will not be recorded on the AEs Section of the CRF except on the condition that, in the Investigator's opinion, these signs and symptoms are caused by any reason different from lack of efficacy of the study product or meet the definition of serious AE.

In the event of a SADE/SAE the Investigator has to:

- Complete the relevant CRF pages and a reporting form with the all available initial information,
- Immediately inform the CRO by telephone,
- Fax the completed report form to the contact person at the CRO or to the Sponsor as soon as possible.

SAE/SADE reporting contacts are on page 4 of this Clinical Investigation Plan.

The Investigator is responsible for ensuring the follow-up of any subject who experiences an SAE/SADE during the study. The investigator must re-examine the subject at regular intervals until the symptoms have completely disappeared or stabilized.

15. Vulnerable population

This section is not applicable, since no subject belonging to any vulnerable population will be recruited for participating in this study.

16. Suspension or premature termination of the clinical investigation

Unless premature interruption occurs, the end of the study will be the closure visit at the clinical site.

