#### **9.1.2 Duration of Exposure**

Duration of exposure will be estimated as the number of day under treatment, calculated using the following formula:

$$\text{Last day of treatment} - \text{first day of treatment} + 1$$

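### AE recording can stop when a patient leaves at G3, so crude AE comparisons need observation time beside them if G3 exits differ between arms

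*SAP*

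**What the plan says.** **Exit at G3.** Protocol section 4 says that at G3 "the subject will immediately interrupt the study treatment and the study participation". Protocol 6.1, 6.2.1.2 and 6.2.2 agree, and SAP 4.2 reports the rule as applied.

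**AE window.** Protocol 14.3: "All AEs regardless of severity occurring between recruitment and completion of the study by a subject must be recorded". After exit, two duties remain: follow-up of patients who had an SAE or SADE (14.3), and completion of the end-of-study CRF pages to the extent feasible, with no date set (16.1).

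**Analysis.** SAP 12.2 counts patients with at least one AE, product-related AE, serious AE and severe AE, and patients withdrawn because of an AE. On these counts it says "The comparisons will be analyzed using chi-square test". It also tabulates the total number of events. The patients counted are all those randomised who received at least one dose (SAP 8.3), and analyses are separate by cancer site (SAP 9.1).

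**Exposure.** SAP 9.1.2: "Duration of exposure will be estimated as the number of day under treatment". No AE analysis uses that variable, section 12.1 is a heading without text, and the table list in SAP 14 has no table of exposure or observation time.

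**G3 rates.** Protocol section 3 reports that at week 5 "patients with G2 and G3 dermatitis were about 52% and 10% in the historical cohort", against 15% and 2% in the Xonrid pilot.

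**The concern.** A crude proportion with at least one AE compares arms fairly when both are watched for the same time. Here the length of observation is itself an outcome. A patient who exits at day 35 of a planned 63 is observed for AEs for 28 fewer days, and the patients affected are those with the worst skin. If the gel changes how often G3 occurs, its efficacy alters the AE window and so enters the safety comparison. Total event counts are more directly affected than proportions, because under a constant hazard they scale with time observed. As planned, a reader of the report would see the AE tables without the observation time behind them.

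**Working it through.** **1. The plan's own figure.** The documents give no figure for the AE comparison, so the sample size serves only to fix the number per arm. Protocol 7.1 claims that "a two group chi-square test with a 0.05 two-sided significance level will have 80% power" with 18 per group. The inputs are Group B, "38.2% of the patients treated with SOC preemptive treatment according to MASCC guidelines did not reach G2 radiation dermatitis at week 5", and Group A, "a proportion of 82.9% in the Group A".

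- Mean proportion: (0.382 + 0.829)/2 = 0.6055.
- n = [1.96 × √(2 × 0.6055 × 0.3945) + 0.8416 × √(0.382 × 0.618 + 0.829 × 0.171)]² / 0.447² = (1.355 + 0.517)² / 0.1998 = 17.5, so 18 per group (power 81.1%).
- With 10% dropout: 18/0.9 = 20.

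The figure reproduces. It concerns the primary endpoint and neither supports nor weakens this point.

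**2. Inputs for the AE check.**

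- From the documents: full follow-up F = 63 days (head and neck) or 56 days (breast), Protocol 6.4.1; share leaving at G3, g = 0.10 (Group B) and 0.02 (Group A), Protocol section 3.
- Assumed, because the documents do not give them: exit day t = 21, 28 or 35; true proportion p with at least one AE at full follow-up = 20%, 50% or 80%; the same constant AE hazard in both arms and in G3 patients; no AE captured after exit.

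**3. Formulas.**

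- Mean observed days = (1 − g)F + g·t.
- Observed proportion = (1 − g)p + g[1 − (1 − p)^(t/F)].
- Gap between arms = (0.10 − 0.02) × [(1 − p)^(t/F) − (1 − p)].

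**4. At the documents' G3 figures.** Head and neck, t = 35, p = 0.5:

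- Days: B 0.90 × 63 + 0.10 × 35 = 60.2; A 0.98 × 63 + 0.02 × 35 = 62.4; ratio 0.964.
- An exiting patient's chance of an observed AE: 1 − 0.5^(35/63) = 0.320.
- Proportions: B 0.450 + 0.032 = 48.2%; A 0.490 + 0.006 = 49.6%. Gap 1.4 points.

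Extremes over all the assumed values: smallest 0.08 × (0.8^(35/56) − 0.8) = 0.6 points; largest 0.08 × (0.2^(21/63) − 0.2) = 3.1 points. If every AE fell after the exit day, the gap at p = 0.5 would be 0.5 × 0.08 = 4 points.

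**5. At assumed heavier G3 rates** (not in the documents; exit days 21 to 35, p = 20% to 80%, both sites):

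| G3 exits, B v A | Gap, points |
|---|---|
| 30% v 10% | 1.4 to 7.7 |
| 50% v 20% | 2.1 to 11.5 |

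**6. Effect on the test.** This is an exact enumeration of the uncorrected chi-square at 20 per arm, true AE proportion 50% in both arms, F = 63. The probability of rejection is 4.3% with no truncation and 4.3% at 10% v 2% with exit on day 35. At an assumed 50% v 20% it is 5.8% (exit day 35) or 8.5% (exit day 21).

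**7. Direction.** If G3 patients have k times the AE hazard of the others, their observed proportion is 1 − (1 − p)^(kt/F). This equals p when k = F/t: 56/35 = 1.6, 63/35 = 1.8, 63/21 = 3. At that k the gap is zero; above it the gap reverses.

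**8. How far patient-time helps.** Take an assumed 40% v 10% leaving at day 42 of 63, with 60% of the cumulative hazard H falling after that day and no true difference.

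- Expected events: A (0.90 + 0.10 × 0.40)H = 0.94H; B (0.60 + 0.40 × 0.40)H = 0.76H. Crude ratio 1.24.
- Mean days: A 60.9, B 54.6. Rate ratio (0.94/60.9)/(0.76/54.6) = 1.11.

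The artefact shrinks by more than half but does not vanish.

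**The case against.** - **The effect is small.** At the only G3 figures available the gap is 0.6 to 3.1 points; with 20 per arm one patient is 5 points. This stands, and it limits the point to an improvement.
- **The plan does not build in different G3 rates.** The 10% v 2% compares a pilot with a historical cohort, without randomisation, in head and neck cancer only. The sample size rests on G2, and no breast G3 rate is given. SAP 13 says most patients reached G2, which says nothing about G3. This stands.
- **AEs after G3 may not all be lost.** The end-of-study pages include AE recording (Protocol 6.4.1), and 16.1 asks for them after discontinuation. But 16.1 does not say when they are completed, so the loss is plausible rather than established.
- **Unequal exit would be visible** in the disposition summary, the dropout tables by site and the listing of discontinued patients (SAP 10.1, 14 and 16.1). True, but none of these puts AEs over time observed.
- **Patient-time methods carry their own assumptions.** Rates assume a constant hazard, and Kaplan-Meier censored at exit assumes uninformative exit although severe skin toxicity triggers it. This stands, so they belong beside the crude proportions and should not replace them.

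A reader might infer that the arm with more G3 looks safer by construction. The documents do not support that. It requires unequal G3 rates and an AE hazard in G3 patients that is not raised. Two of the compared categories can also run the other way. Protocol 14.2 equates grade 3 with severe, so if a G3 exit is counted as a severe AE or as a withdrawal because of an AE, the arm with more G3 looks worse. Protocol 14.3 keeps lack-of-efficacy signs out of the AE section with exceptions, and 16.1 lists G3 skin toxicity separately from AEs, so the handling is open.

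**Conclusion.** The structural gap holds: AE observation time depends on skin outcome, and crude AE proportions and event totals are compared or tabulated by arm without it. They are not strictly comparable if G3 exit differs between arms. At the documents' head and neck figures the proportions differ by about 1 to 3 points with little effect on the test at 20 per arm. That estimate assumes equal constant hazards, exit at days 21 to 35 and no AE capture after exit; applying it to breast cancer or to G3 after week 5 is a further assumption. The direction is not fixed, and larger gaps come only from G3 rates that the documents do not give. This is a cheap improvement to the safety reporting.

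**What to change.** **SAP, usable now** (the final analysis follows database lock, SAP 6.2):

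- In 12.1, report days under AE observation by arm and site, with a definition of when observation ends after a G3 exit.
- In 12.2, keep the crude proportions. Beside them give AE events and first events per patient-time, with a rate ratio and 95% CI. For total events, the interval should allow for repeated events in one patient. State that exit at G3 may be informative and that the hazard may not be constant.
- State whether a G3 exit counts as a severe AE, as a withdrawal because of an AE, or as neither.

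**Protocol** (sections 4, 6.1, 6.2 and 16.1): separate the end of data collection from the end of study treatment at G3, leaving the treatment rule unchanged. AEs would then continue to be recorded, flagged as post-G3, to day 56 or 63 in consenting patients. This would remove most of the problem at its source. The SAP, dated 18 December 2018, describes enrolment as complete, so this applies only where it is still feasible.

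**Cost:** one extra table and some wording in the SAP; a post-G3 flag and an amendment if the protocol change is made. AEs after G3 arise on other treatment and need to be read with that in mind.
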